5.5.2 Dose delays

If at the time of the next planned administration, any drug-related toxicities are still present and have not resolved to Grade \leq 1 or returned to baseline, the infusion should be delayed for up to two weeks until these toxicities have resolved to Grade \leq 1 or returned to baseline. If there is no recovery after a two week delay (i.e. the time between doses is three weeks or more), the patient should be withdrawn from the study. Dose delay for reasons other than toxicity should be avoided if possible, but delays resulting from intercurrent illness will not necessarily mandate discontinuation of study treatment.

5.5.3 Dose interruptions

Interrupting or slowing the rate of the infusion may help control infusion-related symptoms (other than anaphylaxis). The infusion may be resumed when symptoms abate. Should repeated infusion interruptions be required, the infusion may be interrupted overnight and resumed the following day. However, this is expected to be a rare occurrence. If a patient receives less than 80% of the planned infusion, then they will be evaluable for safety, but they will not be evaluable for dose review decisions. A patient must have received $>80\%$ of 3 infusions before being evaluable for dose review decisions unless otherwise agreed with the TSG.

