3.3.1 Dose limiting toxicity (DLT)

Dose limiting toxicity is defined as any of the following events occurring in the first 3 weeks of IMP administration that are considered to be probably or highly probably related to MOv18 IgE:

(For dose-independent significant toxicity, see Section 3.3.2)

Non-haematological toxicity

- Any other drug-related non-haematological Grade 3 or 4 toxicity EXCLUDING:
 - Grade 3 or 4 nausea or vomiting, in patients who have not received optimal treatment with anti-emetics
 - Grade 3 or 4 diarrhoea in patients who have not received optimal treatment with anti-diarrhoeals e.g. loperamide and/or codeine
 - Transient Grade 3 biochemical abnormalities that are asymptomatic and considered not to be clinically significant
 - Grade 3 fatigue
- Fatal event

Haematological toxicity

- Grade 4 neutropenia ($ANC < 0.5 \times 10^9/L$) for ≥ 5 days duration *see note
- Febrile neutropenia (fever of unknown origin without clinically or microbiologically documented infection with Grade 3 or 4 neutropenia [$ANC < 1.0 \times 10^9/L$] and fever $\geq 38.5^\circ C$)
- infection (documented clinically or microbiologically) with Grade 3 or 4 neutropenia ($ANC < 1.0 \times 10^9/L$);
- Grade 4 thrombocytopenia (platelets $< 25 \times 10^9/L$)
 - a) for ≥ 5 days *see note, or
 - b) associated with active bleeding, or
 - c) requiring platelet transfusion.

* In the event of a Grade 4 neutropenia or Grade 4 thrombocytopenia, a full blood count must be performed at least five days after the onset of the event to determine if a DLT has occurred. Continue to monitor the patient closely until resolution to Grade 3 or less.

Note that:

- Isolated cutaneous toxicity (urticaria or other skin symptoms/signs) without any associated systemic symptoms or signs and without serum tryptase elevation may not be considered a DLT, if agreed by the Trial Steering Group (TSG) (see Section 3.6 for information regarding the Trial Steering Group). Such patients require premedication (at least for the first subsequent dose) and very close observation if they are given further doses of MOv18 IgE;

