5.3.1 Study drug administration

All patients will receive their first two doses of MOv18 IgE as an IV infusion over 90 minutes (+/-15 mins). A shorter infusion time for subsequent doses of 60 minutes (+/-10 mins) will be allowed if no infusion-related reactions or other allergic reactions are encountered after two doses have been administered. A longer infusion time for subsequent infusions will also be allowed if required in order to manage infusion related cutaneous toxicity. Patients should remain in the clinic for observation for at least one hour after every dose of MOv18 IgE.

The study will be undertaken at investigational centres staffed and equipped to manage medical emergencies and with intensive care facilities. If the patient experiences an event related to study drug that requires intensive clinical care, the Sponsor must be notified immediately.

Patients will be admitted overnight after the first two doses to facilitate intensive safety monitoring procedures. At the investigator's discretion, the requirement for admission may be waived for the second dose if the patient experiences no clinically important adverse events related to MOv18 IgE during the infusion and observation period.

Pre-medication will be administered prior to the first dose in later cohorts if deemed medically appropriate. See Section 5.4

The patient will be intensively monitored during their first two infusions, with measurement of vital signs (blood pressure, pulse rate and temperature) every 15 minutes from the start of the infusion until 30 minutes after completion of the infusion. If no changes are seen, during the first two infusions, then for subsequent infusions vital signs will be assessed 15 minutes and 30 minutes after completion of the infusion. Continuous monitoring with a pulse oximeter is required throughout each infusion until 30 minutes after completion.

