If the patient experiences symptoms suggestive of an infusion-related reaction or cytokine release (such as fever, chills, and myalgia), the infusion must be slowed or interrupted and the patient must be treated with oxygen, paracetamol, antihistamines, fluid resuscitation and/or steroids, as clinically indicated. If the reaction does not respond to these conservative measures or is > Grade 2 in severity, the algorithm for the treatment of anaphylaxis must be followed (Appendix 4). Note that for the purposes of this protocol, infusion-related symptoms and signs (such as fever, myalgia, and hypotension) will be recorded and graded individually according to NCI-CTCAE Version 4.02. Grading of systemic mast cell degranulation (anaphylaxis) is defined in Appendix 5 and grading of cytokine release syndrome is defined in Appendix 6, but the distinction between these two events and grading of these events will be performed only in retrospect when results of serum tryptase assays are available, and will thus not be relevant for the management of acute events at the time of infusion. A blood test for measurement of serum tryptase will be taken on completion of all infusions. Additional blood samples for serum tryptase levels should be taken in patients who experience a suspected anaphylactic reaction, such as urticaria and/or severe infusion-related symptoms necessitating interruption or discontinuation of the infusion. Additional samples for serum tryptase should also be taken for patients with a positive skin prick test (see study lab manual and protocol section 7.2 for time points). For details on grading and reporting of infusion-related events and anaphylaxis see Section 7.2.5.

The following medications must be available at the bedside for use in case of an immune-mediated reaction: epinephrine (0.5-1mL IM injection 1:1000), chlorphenamine 10 mg IV/IM injection, paracetamol 1 g orally, hydrocortisone 200 mg IM or IV; oxygen (see 16.4 Appendix 4: Treatment of Anaphylaxis).

For patients who are enrolled in an intra-patient escalation cohort, and receive a higher dose in Cycle 2, the following additional measures will apply:

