5.5 Dose modifications

5.5.1 Dose reductions

Patients experiencing a DLT at any time will have their MOv18 IgE treatment withheld until toxicity resolves to baseline or Grade 1. After resolution, MOv18 IgE may be recommenced at the same dose.

Dose reduction is not generally envisaged but if required (for DLT or other toxicities, other than Grade \geq 2 anaphylaxis) will be to the next lowest dose according to the dose escalation scheme (Table 1). Only one dose reduction is allowed per patient. Individual patient dose reductions should be discussed and agreed with the CDD.

Patients experiencing Grade \geq 2 anaphylaxis (see Appendix 5) must discontinue study medication (see Section 3.3.2 and 3.4.2). As per Section 3.4.2, the TSG will also take into consideration any equivocal or Grade 1 events, should these occur. For other infusion reactions (see Appendix 6), continuation of study drug at the same dose level may be appropriate but must be discussed with the TSG.

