7.2.5 Infusion reactions and anaphylaxis

Patients should be assessed carefully for infusion-related reactions. Since it may not be apparent at the time whether a patient is having a reaction due to cytokine release or mast cell degranulation, and since NCI-CTCAE Version 4.02 criteria overlap for cytokine release syndrome, allergic reaction and anaphylaxis, it is proposed that:

- All infusion-related events are reported as individual AEs (e.g. fever, nausea, myalgia or hypotension). Time of onset and worst grade (according to NCI-CTCAE Version 4.02) should be noted for each event.
- Subsequently, infusion-related events associated with an elevation in serum tryptase will be categorised according to the grading criteria outlined in Appendix 5 for IgE-associated mast cell degranulation (anaphylaxis).
- Urticaria is a characteristic feature of anaphylaxis and is to be regarded with suspicion. Patients who experience any of the following events should have additional samples taken as outlined below:

- Urticaria; symptoms/signs suggestive of mast cell degranulation; a suspected anaphylactic reaction; signs and symptoms suggestive of a severe allergic-type reaction; severe infusion-related symptoms necessitating interruption or discontinuation of the infusion.

Additional Samples:

NB: the additional samples outlined below can replace the existing samples in the Schedule of assessments, if the timepoints overlap. Please take all other samples as per schedule in section 7.6.

- Serum tryptase (immediately*, 2 and 6** hours post onset),
- BAT assay (immediately* post onset, in replacement of existing 2 hour timepoint in schedule),
- PK (immediately*, 2 and 6** hours post onset),
- [REDACTED]

*Or as soon as possible post onset.

**6 hour samples may be omitted *if* impracticable and clinical suspicion of systemic toxicity is low. This is at the discretion of the treating clinician.

- If a patient clearly shows a pattern of simple urticaria with two separate infusions, with no other systemic signs or symptoms and no other features of anaphylaxis (including normal tryptase results and normal BAT assay results) then, following discussion and confirmation with Sponsor, there may be no requirement for additional samples.
- [REDACTED]
- [REDACTED]
- [REDACTED]
- Infusion-related events without an elevation in serum tryptase will be categorised as cytokine release syndrome according to NCI-CTCAE Version 4.02 (Appendix 6).

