16.4 Appendix 4: Treatment of Anaphylaxis

[Based on (Simons et al., 2011a; Simons et al., 2011b)]

If the patient experiences symptoms suggestive of an infusion-related reaction or cytokine release, the infusion must be slowed or interrupted, and the patient must be treated with oxygen, paracetamol, antihistamines, fluid resuscitation and/or steroids, as clinically indicated.

Anaphylaxis should be suspected if:

- There is a sudden onset and rapid progression of symptoms
- The reaction is > Grade 2 in severity (see Appendix 5) and fails to respond to the conservative measures outlined above

or

- The reaction is > Grade 2 in severity and associated with rapid onset of urticaria (within 10 minutes of starting the infusion).
- The patient experiences life-threatening airway and/or breathing and/or circulation problems

If anaphylaxis is suspected based on these criteria:

- Summon help (resuscitation team)
- Stop the infusion
- Inject epinephrine (adrenaline) intramuscularly into the mid-anterolateral aspect of the thigh
 - 0.5-1mL 1:1000 epinephrine
 - Record the time of dose and repeat it in 5-15 minutes if needed (e.g. because of progressing hypotension and/or laryngeal oedema).
- Place the patient on his/her back or in a position of comfort if there is respiratory distress and/or vomiting; elevate the legs
- If not already started, give high-flow (6-8 L/min) supplemental oxygen by face mask
- If not already started, give 1-2 litres of 0.9% isotonic saline rapidly (e.g. 5-10 mL/kg in the first 5-10 minutes), as clinically indicated
- Give chlorphenamine 10mg IM or slow IV
- Consider hydrocortisone 200mg IM or slow IV
- Consider bronchodilators if clinically indicated.

Cardiac arrest associated with anaphylaxis

- If indicated, perform cardiopulmonary resuscitation as per Adult Life Support guidelines

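### Section 5.5.3 removes under-dosed patients from dose review with no exception for a DLT, which contradicts the DLT counts in Section 3.4.1, Table 2 and Section 5.4.2

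*Protocol*

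**What the plan says.** Section 5.5.3 contains two evaluability sentences. The first covers a patient who receives less than 80% of the planned infusion: "they will be evaluable for safety, but they will not be evaluable for dose review decisions". The second requires more than 80% "of 3 infusions before being evaluable for dose review decisions unless otherwise agreed with the TSG". The steering group (TSG) override is attached only to the second sentence, and neither sentence mentions DLTs.

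Other sections treat the count differently:

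- Section 3.3.1 defines a DLT by event type, a three-week window and causality. It sets no minimum amount infused, and its list includes a fatal event.
- Section 3.4.1, Table 2 and Section 5.4.2 act on the number of patients with a DLT, with no exposure condition.
- Section 3.5 (repeated in 13.2) and Section 5.4.3 ask for three doses without a DLT. Section 5.4 replaces a patient withdrawn before three doses only if there was no DLT and no positive skin prick test.

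**The concern.** A DLT can be the reason why a patient falls short of the exposure condition. If that patient then drops out of dose review, the DLTs at risk of not counting are those severe enough to end dosing. The escalation rule works on very small numbers (two DLTs in three or six patients), so removing one patient changes the fraction the rule is applied to. In a first-in-human trial the numerator and denominator of the stopping rule should be fixed before the outcome is known. Here two parts of the same protocol give different answers, and no sentence says which governs.

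**Working it through.** **Step 1: can a DLT patient fall below the 5.5.3 condition under the protocol's own rules?**

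- *Fatal DLT.* A patient who dies after infusion 1 or 2 has at most two infusions and can never have more than 80% of three. No further assumption is needed.
- *Toxicity that does not resolve.* Section 5.5.1: "Patients experiencing a DLT at any time will have their MOv18 IgE treatment withheld until toxicity resolves to baseline or Grade 1". Section 5.5.2 withdraws a patient whose drug-related toxicity has not recovered after a two-week delay. If that happens before the third infusion, the condition is not met. Withholding alone is not enough, because 5.5.1 goes on to allow dosing to restart after resolution.
- *Infusion reaction.* Under Section 5.3.1, if a reaction does not respond to conservative measures or "is > Grade 2 in severity, the algorithm for the treatment of anaphylaxis must be followed". Appendix 4 includes the step "Stop the infusion", but only once its criteria for suspected anaphylaxis are met. Section 7.2.5 then says: "Infusion-related events without an elevation in serum tryptase will be categorised as cytokine release syndrome". A reaction so classed, at Grade 3 or 4 and probably or highly probably related, falls under the 3.3.1 item "Any other drug-related non-haematological Grade 3 or 4 toxicity EXCLUDING" (its listed exclusions aside). Section 5.5.3 lets an interrupted infusion resume, so only an infusion that stays incomplete matters here. At a constant rate (an assumption), 80% of a 90-minute infusion is 0.80 × 90 = 72 minutes.

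**Step 2: how far do the two counts differ?**

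The protocol states no operating characteristic to reproduce, so this is a direct count. Let *n* be patients treated, *d* patients with a DLT, and *k* the DLT patients below the 5.5.3 condition. All other patients complete three infusions, and nobody is replaced (Section 5.4 does not replace a patient with a DLT).

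Table 2 counts d/n. Literal 5.5.3 counts (d − k)/(n − k).

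| Cohort | n, d, k | Table 2 | Literal 5.5.3 | DLT-free completers, n − d |
|---|---|---|---|---|
| One DLT, under-dosed | 3, 1, 1 | 1/3: accrue three more | 0/2: no row | 2 |
| Two DLTs, both under-dosed | 3, 2, 2 | 2/3: stop | 0/1: row only for Cohorts 1–4 | 1 |
| Expanded cohort, second DLT under-dosed | 6, 2, 1 | 2/6: stop | 1/5: no row | 4 |
| One-patient intra-patient cohort | 1, 1, 1 | 1/1: no row | 0/0: no row | 0 |

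The 0/1 row in Table 2 is restricted to Cohorts 1–4. Section 5.4 reports recruitment complete through Cohort 6, so that row does not apply to the cohorts still to come.

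**Step 3: does the literal reading lead to escalation?**

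- 0/2 and 0/1: two or one DLT-free completers do not reach the three that Section 3.5 needs in a three-patient cohort. Section 5.4.2 also calls for expansion after one DLT and stops escalation after two.
- 1/5: four DLT-free completers do meet the 3.5 minimum. Only the direct DLT text in 5.4.2 and Table 2 stops escalation here.
- 0/0: Section 5.4.1 expands the cohort after any DLT.

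In every count, escalation is blocked provided the DLT text is followed over 5.5.3.

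**The case against.** The strongest reply is that the 80% rule was never meant for DLT patients. Its only worked application, in Section 5.4.3, concerns a patient who received under 80% of the first dose and then tolerated the next two in full; an extra full dose makes that patient evaluable. That fits Sections 3.5 and 5.4, where the three-dose requirement decides who may support escalation as DLT-free. On this view, discarding a drug-related death is a strained reading of one sentence against several others. This largely stands as an account of intent, and most of the text favours counting these DLTs. It does not remove the contradiction: 5.5.3 states its rule without the qualifier used elsewhere, and the only override is discretionary and attached to one of its two sentences.

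Three stronger inferences are tempting, and the documents do not support them:

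- *That DLTs are hidden, or that the trial would escalate past its limit.* The patients remain evaluable for safety, DLTs must be reported within 24 hours (Section 9.2.2), and Table 2 bars further accrual after a second DLT. Escalation probabilities computed by excluding DLT patients and replacing them would have no basis, because neither 5.4 nor 5.6.1 provides for replacing a patient withdrawn for a DLT.
- *That every DLT makes the patient non-evaluable.* Dosing may restart under 5.5.1, and Appendix 4 does not stop the infusion for every reaction above Grade 2.
- *That 5.4 and 5.6.1 conflict on replacement after toxicity short of a DLT.* Section 5.4 makes replacement mandatory in that case. Section 5.6.1 permits replacement for other reasons and does not forbid it here, so both can be followed. The difference is editorial.

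**Conclusion.** The point holds as an internal contradiction that should be fixed. Section 5.5.3 as written takes a patient whose DLT ended dosing early out of dose review, while Sections 3.4.1 and 5.4.2 and Table 2 count that patient. The size is a change of fraction: 1/3 against 0/2, 2/3 against 0/1, 2/6 against 1/5. The last is the most exposed, because there the 3.5 minimum is met and only the DLT text holds the line.

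These counts rest on a literal reading of 5.5.3, no replacement, and full dosing in all other patients. How often a DLT would leave a patient below the condition cannot be taken from the protocol. No wrongful escalation is shown.

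**What to change.** In Section 5.5.3, with a cross-reference in 3.5, state that the requirement for more than 80% of three infusions applies only to patients without a DLT. Add that a patient with a DLT in the DLT window is counted in dose review whatever the amount infused, consistent with 3.5, 5.4, 5.4.2 and Table 2. This settles counting only and leaves dosing and management of reactions untouched.

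Editorial, in the same amendment: align 5.4 and 5.6.1 for withdrawal before three doses because of drug-related toxicity short of a DLT, and assign exactly 80%, which neither sentence of 5.5.3 now covers.

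Cost: a few sentences of protocol wording and no new data. The one downside is that a cohort may reach its DLT limit sooner than under the literal 5.5.3 count.

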5.5.4 Dose discontinuations following positive skin prick tests

In general, patients experiencing a positive skin prick test will be withdrawn immediately from study treatment (i.e. they will receive no further IV MOv18 IgE and will undergo no further skin prick testing). However, IgEs have never been administered into the skin before and it is possible that they may be more likely to provoke a positive reaction than other agents. They may also be more likely to provoke cutaneous reactions (without systemic symptoms) when administered IV. The clinical implications of a wheal and flare reaction following skin prick testing of MOv18 IgE is therefore not clear. Accordingly, it is possible that patients may be able to safely receive IV MOv18 IgE (with prophylactic medication and very careful medical supervision) despite a positive skin prick test.

Prior to Protocol Version 5.0, all patients underwent intradermal testing before IV MOv18 IgE administration. Since Protocol Version 5.0, all patients will undergo skin prick testing (instead of intradermal testing) prior to IV MOv18 IgE administration. It is expected that skin prick testing will avoid “false-positive” tests due to non-specific mast cell reactivity (which may be the cause of positive intradermal tests). A decision on whether to allow IV MOv18 IgE administration despite a positive skin prick test will be made by the TSG following a review of patient data from at least 6 patients who have undergone at least two skin prick tests using MOv18 IgE (assuming the first test is negative). A patient experiencing a positive skin prick test on first administration can also be included in this assessment. If 50% or more of 6 patients experience a positive skin prick test (on first or subsequent exposure), without systemic symptoms or signs or serum tryptase elevation, IV dosing in the presence of a positive skin prick test may be explored with the TSG.

The possibility of IV dosing in the presence of a positive skin prick test may be considered by the TSG again at a later date following enrolment of further patients, depending on emerging data (for example, if positive tests without systemic symptoms or signs or tryptase elevation prevent patients receiving further IV MOv18 IgE despite evidence of anti-tumour activity).

5.6 Duration of treatment

A finite number of doses will be administered to each patient. All patients should receive six weekly infusions (two cycles of three weeks) unless (a) the patient asks to be withdrawn, (b) there is evidence of disease progression, or (c) the patient experiences unacceptable toxicity, or (d) for any other of the reasons for withdrawal from the study listed in Section 11. Patients who receive all six infusions in the Initial Dosing Period are considered to have completed study treatment. The duration of treatment will be approximately six weeks followed by a 70-day (+/- 14 days) follow-up period.

As outlined in Section 3.2, drug supply permitting, patients may continue on treatment into the Maintenance Period. These patients may receive an additional three fortnightly infusions of MOv18 IgE.

For these patients, the total treatment duration would be 12 weeks unless treatment stops early because (a) the patient asks to be withdrawn, (b) there is evidence of disease progression, or (c) the patient experiences unacceptable toxicity, or (d) for any other of the reasons for withdrawal from the study listed in Section 11. Treatment will be followed by a 70 day (+/- 14 days) safety follow-up period.

